6.5.3. Mitigations

Risks have been mitigated to levels as low as reasonably possible (ALARP) for this trial. No prior clinical studies have been performed of SIG-001 to date; however, the constituent sodium alginate cell encapsulation approach and genetically modified ARPE-19 epithelial cells have been studied in humans for over four decades (Section 4.3) (Basta et al., 2011; Bochenek et al., 2018; Calafiore et al., 2006; Jacobs-Tulleneers-Thevissen et al., 2013; Shinichi Matsumoto, Abalovich, Wechsler, Wynyard, & Elliott, 2016; Tuch et al., 2009; Vegas et al., 2016). Although no concerning safety signals have been reported, immune response to allogeneic, non-encapsulated cells and a PFO response to the encapsulating materials have significantly limited their durability. SIG-001 design consists of an inner compartment made of peptide-modified alginates that promote cell adhesion, and an outer layer of modified alginates that acts as both a physical barrier to protect the genetically modified ARPE-19 cells from immune damage and to prevent a PFO response.

The study will not exceed **CCI** of SIG-001 spheres which is a volume approximately 3- to 10-fold lower than those administered in nonclinical studies of SIG-001.

Based on the dose modelling results discussed in Section 6.5.1, the volumes of SIG-001 to be administered in this study have a low risk for over-exposure to FVIII (e.g. FVIII levels well above 150% of normal), even at the highest SIG-001 dose of up to **CCI** (Cohort 3, Dose 3).

To decrease anaesthesia and laparoscopy procedure-related risks, only patients with a BMI of <35, with acceptable hematologic and blood chemistry values at baseline, who are deemed by the Investigator to be healthy to undergo the anaesthesia and laparoscopic procedure are eligible for this study. In addition, to decrease the risk of abdominal-related adverse events, patients with a medical history of adhesions, IBD or any other comorbidity potentially increasing the risk of abdominal adhesions are excluded.

Non-contrast abdominal MRI will be performed as part of this study. MRI involves non-ionising radiation, and study MRI exams will not require administration of contrast agents (e.g. gadolinium) or other medications. If a patient is unable to undergo an MRI, an abdominal ultrasound will be done instead. Study MRI and ultrasound exams are not expected to involve greater risk than routine MRI and ultrasound exams.

PROTOCOL

Title: Safety and Efficacy of Encapsulated Allogeneic FVIII Cell Therapy in Haemophilia A
Study No. SIG-001-121

To further limit risks in this study, patients with known sensitivities to FVIII therapies, alginates (seaweed), barium and barium products (including barium contrast agents), and/or products containing FBS are excluded. FBS is predominantly removed using extensive washing during SIG-001 manufacturing. Only patients with haemophilia A who have achieved ≥ 150 exposures to FVIII and have no past or current titres of FVIII inhibitor are eligible to participate in this study. Treatment-naïve patients without known ability to tolerate FVIII therapies are excluded. Lastly, SIG-001 produces human FVIII with the same amino acid sequence of commercially available recombinant FVIII products that have a well-established safety profile (Moroctocog alfa or BDDrFVIII; trade names ReFacto®, XYNTHA®).

Throughout the study patients retain access to on-demand FVIII for any bleeding episodes, perioperative management for surgery or other medical procedures, or prior to vigorous physical activity. Criteria for re-starting prophylactic therapy after SIG-001 administration are described in Section 7.5.1.

6.6. Stopping Criteria

6.6.1. Individual Stopping Criteria

SIG-001 involves an intraperitoneal administration. In the event of an unforeseen safety event, the SRC will evaluate the issue. All patients who have already received SIG-001 will remain in the trial and continue to be followed for the duration of the study per the Schedule of Assessments (Table 2 Schedule of Assessments).

6.6.2. Dose Limiting Toxicities and Cohort and Study Stopping Rules

DLTs are defined as the AEs and SAEs listed below. DLTs will be recorded from first patient administration until 8 weeks after last patient administration of SIG-001. All AEs/SAEs will be graded and reported as per Section 12 Safety and Adverse Events.

Any occurrence of the DLTs listed below will trigger an ad hoc evaluation by the SRC and further dosing or dose escalation in the trial will be halted.

- Any death
- Any SAE that is considered possibly or probably related to SIG-001, which is deemed to pose unacceptable risk to study participants
- Any surgical SAE that is considered possibly or probably related to the anaesthesia or laparoscopic procedure, deemed to pose an unacceptable risk to study participants, and occurs in more than 2 patients at any dose level
- Any Grade III-IV toxicity assessed as possibly or probably related to the study product. Examples include, but are not limited to:
 - Inhibitor development with persistent titres > 0.6 NBU/mL
 - Persistent abdominal pain
 - Persistently abnormal laboratory values, such as:
 - Alanine aminotransferase (ALT) elevations $> 5 \times$ upper limit of normal (ULN) in the absence of a concomitant bilirubin increase

PROTOCOL

Title: Safety and Efficacy of Encapsulated Allogeneic FVIII Cell Therapy in Haemophilia A
Study No. SIG-001-121

- ALT elevations $> 3 \times \text{ULN}$ in the presence of a total bilirubin increase $> 2 \times \text{ULN}$ or an international normalized ratio (INR) > 1.5 without findings of cholestasis or other alternate aetiology to explain the elevations
- ALT elevations $> 3 \times \text{ULN}$ with the appearance of fatigue, nausea, vomiting, right upper quadrant pain or tenderness, fever, rash and/or eosinophilia ($> 5\%$)
- Any thrombotic event
- Any peritonitis
- Abdominal adhesions/fibrosis
- Supratherapeutic levels of FVIII activity (above 150 IU/dL, or $> 150\%$ activity)
- An overall pattern of clinically significant changes in any safety parameter, considered to be potentially related to the study product that represents a safety concern.

The stopping criteria for this study is the occurrence of one or more of the DLTs listed above. The study will be halted if a stopping criterion is met. If the Sponsor suspends the trial, the Investigators, Ethics Committees (IEC/IRB) and Regulatory Authorities will be promptly notified in writing with the reason for suspension/termination. If, following a safety review by the SRC, it is considered appropriate to restart dosing in the trial, Regulatory Authorities and Ethics Committees will be notified accordingly. Any proposal to restart dosing in the trial will require Regulatory Authorities and Ethics Committees approval of a substantial protocol amendment prior to implementation.

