6.3. Cohorts and Grouping

Up to three (3) escalating dose cohorts are planned. Each cohort will initially include up to three patients and can be expanded to enrol up to three additional patients; thus, up to 6 patients may be enrolled at a single dose level.

- Cohort 1 (Dose 1): CCI of SIG-001 spheres
- Cohort 2 (Dose 2): CCI of SIG-001 spheres
- Cohort 3 (Dose 3): CCI of SIG-01 spheres

For a full description of the rationale for dose selection, refer to Section 6.5.1.

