6.4. Dose Escalation Design

Patients will be enrolled in one of 3 escalating dose cohorts. Dosing will be staggered by at least 8 weeks for the first 3 patients enrolled in the study. Thereafter, doses will be staggered by at least 4 weeks for the remaining patients in each dose cohort and between dose cohorts. Cohort expansion does not require staggered enrolment. Following SIG-001 administration, safety and efficacy parameters (FVIII activity) through at least the Week 8 visit (first 3 patients) and at least the Week 4 visit (for the remaining patients in any dose cohort and between dose cohorts) will be reviewed by the Safety Review Committee (SRC) prior to dosing any additional patients (Section 11.1).

Decisions regarding dose escalation will be made by the SRC based on review of safety and FVIII activity data of the preceding patient(s) and/or cohort(s) and the Dose Escalation Decision Tree (Figure 3). Dose escalation will occur only if no dose-limiting toxicities (DLTs) and/or clinically-relevant safety issues have been noted. FVIII activity will be reviewed to inform the dose selection (volume of spheres) for the next cohort.

After the first dose (Dose 1, CCI of SIG-001 spheres), the dose may be increased (e.g. planned Dose 2 & 3) or decreased/de-escalated (Dose -1). No dose increase will be >2-fold higher than a dose level previously found to be safe, and no dose will exceed the maximum dose of CCI.

If any patient achieves FVIII activity >100 IU/dL (equivalent to >100% normal FVIII activity) no further dose escalation will occur. Dosing may proceed at the same level or at a lower level.

PROTOCOL

Title: Safety and Efficacy of Encapsulated Allogeneic FVIII Cell Therapy in Haemophilia A
Study No. SIG-001-121

Cohort 1, Dose 1

If the starting dose in the first patient in Cohort 1, Dose 1 is safe and tolerated and FVIII activity is ≥ 5 IU/dL (equivalent to $\geq 5\%$ normal FVIII activity) at Week 8, the next 2 patients will be administered the same dose and followed for safety and efficacy per the Schedule of Assessments (Table 2 Schedule of Assessments). SIG-001 administration for Patients 2 and 3 will be staggered to include a safety review at least 8 weeks after SIG-001 administration.

If no DLTs or clinically-relevant safety issues occur following safety review of Patient 1 Cohort 1 data but FVIII activity in Patient 1 Cohort 1 is <5 IU/dL at Week 8, dose escalation may occur, and the study will progress to Cohort 2, Dose 2.

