Doses will be staggered by at least 8 weeks for the first 3 patients enrolled in the study. Thereafter, doses will be staggered by at least 4 weeks for the remaining patients in any dose cohort and between dose cohorts.

Cohort 2, Dose 2

If the starting dose in the first patient in Cohort 2, Dose 2 is safe and tolerated, the next 2 patients will be administered the same dose via a staggered approach with a safety review after SIG-001 administration, i.e. Dose 2, if:

- 1) FVIII activity in Cohort 2 Patient 1 is ≥ 5 IU/dL, or
- 2) FVIII activity in Cohort 2 Patient 1 is <5 IU/dL but FVIII activity in Cohort 1 Patient 2 or Cohort 1 Patient 3 is ≥ 5 IU/dL

The study will proceed to the highest dose, i.e. Cohort 3, Dose 3, if no DLT or clinically-relevant safety issues occur and:

- 1) FVIII activity in Cohort 1 Patient 1 is <5 IU/dL and FVIII activity in Cohort 2 Patient 1 is also <5 IU/dL, or
- 2) FVIII activity in Cohort 2 Patient 1 is <5 IU/dL, and FVIII activity in Cohort 1 Patients 2 and Patient 3 is <5 IU/dL.

PROTOCOL

Title: Safety and Efficacy of Encapsulated Allogeneic FVIII Cell Therapy in Haemophilia A
Study No. SIG-001-121

Cohort 3, Dose 3

If the starting dose in the first patient in Cohort 3, Dose 3 is safe and tolerated and no DLT or clinically-relevant safety issues occur, the next 2 patients will be administered the same dose via a staggered approach with a safety review after SIG-001 administration, i.e. Dose 3, if:

- 1) FVIII activity in Cohort 3 Patient 1 is ≥ 5 IU/dL, or
- 2) FVIII activity in Cohort 3 Patient 1 is < 5 IU/dL but FVIII activity in Cohort 2 Patient 2 or Cohort 2 Patient 3 is ≥ 5 IU/dL.

[figure not shown]
If FVIII activity in Cohort 3 Patient 1 is < 5 IU/dL and all prior patients had FVIII activity < 5 IU/dL, no further patients will be dosed and enrolment will be stopped. This dose escalation algorithm is intended to monitor patient safety while minimizing patient exposure to subtherapeutic SIG-001 doses. Cohort expansions (up to 3 additional patients) can be initiated after one dose cohort has completed at least 8 weeks of follow-up or after all dose cohorts have completed at least 4 weeks of follow-up. Cohort expansion may be triggered in order to collect additional information regarding safety and efficacy. Decisions regarding cohort expansions will be made by the SRC.

PROTOCOL

Title: Safety and Efficacy of Encapsulated Allogeneic FVIII Cell Therapy in Haemophilia A
Study No. SIG-001-121

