11. STUDY SPECIFIC COMMITTEES

11.1. Safety Review Committee (SRC)

A SRC composed of site Investigators, the Sponsor's representative and at least one independent individual with relevant experience in clinical research will be established. The SRC will review safety and efficacy on an ongoing basis. The SRC will review safety and efficacy parameters through at least the Week 8 visit for the first 3 patients enrolled in the study and at least the Week 4 visit for the remaining patients in any dose cohort, between dose cohorts, and for any cohort expansion. Additionally, the SRC will review all SAEs in an ongoing manner. The SRC may also meet on an ad hoc basis. Should a safety signal arise, the SRC will promptly convene for further assessment of subject safety. Notification of all SRC meetings and meeting outcomes will be sent to all participating sites. Additional information regarding membership and meeting frequency will be included in the *SRC Charter*.

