12.1.7. Relationship

Each AE will be assessed as to its relationship to the Investigational Product and its relationship to the laparoscopic procedure, based on the following criteria:

- Definitely Related: An AE, including laboratory test abnormality (if applicable), in which there is no uncertainty in its relationship
- Probably Related: There is strong medical evidence to suggest that the AE is related
- Possibly Related: There is medical evidence to suggest that there is a reasonable possibility that the AE may be related. However, other medical explanations cannot be excluded as a possible cause
- Unlikely Related: There is no medical evidence to suggest that the AE may be related, or there is another more probable medical explanation
- Not Related: The AE can be determined with certainty to have no relationship

All events assessed as unlikely related to the Investigational Product will be considered unrelated for the purpose of regulatory reporting. All events assessed as possibly or probably related to the Investigational Product will be considered related for the purpose of regulatory reporting.

The relationship assessment of possibly related will be used as the default assessment in the situation when the relationship assessment is omitted by the Investigator and until the relationship assessment is reported by the Investigator.

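### The surgical-SAE stopping rule counts patients separately at each dose level, which leaves a narrow gap when procedural harm is spread across doses

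*Protocol*

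**What the plan says.** Protocol 6.6.2 lists the DLTs, and the occurrence of any one of them is the study's stopping criterion. The surgical item has three conditions: the SAE is possibly or probably related to anaesthesia or laparoscopy, and it is "deemed to pose an unacceptable risk to study participants, and occurs in more than 2 patients at any dose level". The parallel product item has no patient count: "Any SAE that is considered possibly or probably related to SIG-001, which is deemed to pose unacceptable risk to study participants". The item on an overall pattern of safety changes is tied to the study product, so it does not cover harm attributed only to the procedure. No listed item adds procedural SAEs across doses.

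On cohort size, 6.3 says "Each cohort will initially include up to three patients and can be expanded to enrol up to three additional patients", and 7.2 caps enrolment at 18. Section 6.4 lets a dose be left after one patient; one route to Dose 3 is that "FVIII activity in Cohort 1 Patient 1 is <5 IU/dL and FVIII activity in Cohort 2 Patient 1 is also <5 IU/dL". It also permits a lower Dose -1. Expansions need no staggering, and "Cohort expansions (up to 3 additional patients) can be initiated after one dose cohort has completed at least 8 weeks of follow-up".

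Other protections bear on the same events. Section 6.4: "Dose escalation will occur only if no dose-limiting toxicities (DLTs) and/or clinically-relevant safety issues have been noted". Section 11.1: "Additionally, the SRC will review all SAEs in an ongoing manner". Section 12.1.7, when the investigator omits causality: "The relationship assessment of possibly related will be used as the default assessment".

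**The concern.** The item exists to catch recurrence of serious procedural harm, but its count restarts at every dose. Per-dose counting suits a toxicity driven by dose. Here the hazard is mainly general anaesthesia and laparoscopy. Section 9.2.3 describes one approach for every administration, with sponsor-supplied trocar and catheter and a surgeon trained for the study. Section 4.5 states the procedural risk once, without reference to dose.

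An unexpanded cohort of three meets the rule only if all three patients are affected. A cohort of one or two cannot meet it. Two affected patients at each of three doses leave it unmet. At stake is whether a third patient with a procedural SAE already judged an unacceptable risk stops dosing by rule, or only if the SRC chooses to stop. The point is confined to non-fatal SAEs attributed to the procedure and not to the product.

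**Working it through.** **Inputs from the protocol.** Threshold: at least 3 patients at one dose level (6.6.2). Cohort size: 3 initially, up to 6 (6.3). Maximum: 3 × 6 = 18, which agrees with 7.2. No procedural SAE rate is given, and 4.5 expects risk no greater than routine diagnostic laparoscopy. The per-patient rate p of an unacceptable-risk procedural SAE is therefore **assumed** at 5%, 10% and 20%; the low end is closest to the protocol's expectation.

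**Step 1, no rate needed.** The largest total with at most 2 per dose over three doses is 2 + 2 + 2 = 6. That is 6/18 = 33% of full cohorts or 6/9 = 67% of initial cohorts. A seventh affected patient must put 3 at some dose.

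**Step 2, ignoring the bar on escalation.** Patients are independent with common p, and any qualifying surgical SAE counts. Let q(n) = P(Bin(n, p) ≥ 3).

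- Per-dose rule: 1 − ∏(1 − q(nᵢ)). Cumulative rule: q(Σnᵢ).
- Example, p = 5%: q(6) = 1 − 0.95⁶ − 6(0.05)(0.95⁵) − 15(0.05²)(0.95⁴) = 0.00223. For 6-6-6 the per-dose rule gives 1 − (1 − 0.00223)³ = 0.0067, and the cumulative rule gives q(18) = 0.0581.

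**Step 3, with the bar on escalation working fully.** Assume the next dose is opened only if the initial three patients had no such event, which has probability c = (1 − p)³. Let r be the highest dose reached and x the events among its initial three. The weight is c^(r−1) × P(Bin(3, p) = x), with x ≥ 1 for r = 1 or 2 and x ≥ 0 for r = 3.

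- *No expansion.* All earlier cohorts are clean, so both rules need x = 3 at the last dose. Both give p³(1 + c + c²), which is 0.03%, 0.2% and 1.4% at 5%, 10% and 20%. The rules are identical.
- *Every reached dose then expanded to 6.* Given r and x, the per-dose rule has probability 1 − (1 − p³)^(r−1) × [1 − P(Bin(3, p) ≥ 3 − x)]. The cumulative rule has P(Bin(3r, p) ≥ 3 − x).

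Contributions from r = 1, 2, 3:

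| p | Per-dose | Cumulative |
|---|---|---|
| 5% | 0.0021 + 0.0018 + 0.0018 = 0.0058 | 0.0021 + 0.0055 + 0.0144 = 0.0220 |
| 10% | 0.0151 + 0.0112 + 0.0095 = 0.0358 | 0.0151 + 0.0302 + 0.0589 = 0.1042 |
| 20% | 0.0948 + 0.0501 + 0.0297 = 0.1746 | 0.0948 + 0.1081 + 0.1158 = 0.3187 |

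**Summary of halt probability, per-dose to cumulative**

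| Scenario | 5% | 10% | 20% |
|---|---|---|---|
| 3-3-3, bar works, no expansion | no change | no change | no change |
| Bar works, every reached dose expanded to 6 | 0.6% to 2.2% | 3.6% to 10% | 17% to 32% |
| 6-6-6, escalation proceeds despite events (upper bound) | 0.7% to 5.8% | 4.7% to 27% | 27% to 73% |

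**The case against.** The strongest reply is that 6.4 already stops the sequence. Its bar on escalation covers clinically relevant safety issues as well as DLTs, is not limited to product-related events and needs no count. A surgical SAE judged an unacceptable risk would ordinarily qualify, so one event blocks the next dose. Reaching 2-2-2 through initial cohorts alone would take two escalations past such events. The one-patient routes carry the same condition. This stands, and it is why the rules do not differ for unexpanded initial cohorts. A reader might infer that six such patients could accumulate unchecked, or that one-patient cohorts leave the first patients unprotected. The protocol supports neither: staggered patients are reviewed before further dosing, the SRC reviews all SAEs, and it decides on every expansion.

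Other DLTs also take part of the load. Any death counts. So does a single unacceptable-risk SAE possibly related to both product and procedure, and an omitted causality assessment defaults to possibly related. Thrombosis, peritonitis and adhesions are listed too, although the layout of the text does not show whether they stand alone or are examples of product-related Grade III-IV toxicity.

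A per-dose count is also a coherent choice for a dose-limiting toxicity. Sphere and buffer volumes rise with dose, and laparoscopic technique varies by site. That supports keeping a per-dose tally, but not discarding earlier events from the halt count.

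Four situations remain in which the bar on escalation does not do this work:

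- unstaggered expansions at more than one dose;
- a move down to Dose -1, which is not an escalation;
- events that arise after the escalation review;
- an SRC that does not treat one or two such SAEs as barring escalation, a reading that the more-than-2 tolerance invites.

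In these, stopping rests on SRC judgement, with no defined count across doses.

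**Conclusion.** The point holds as a narrow gap with a cheap remedy. The per-dose count does not halt dosing by rule when three or more patients at different doses have non-fatal, purely procedural SAEs already judged an unacceptable risk. The limit of six such patients over three dose levels needs no assumption about rates.

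The size depends on assumed rates, independence between patients and how strictly the bar on escalation is applied. With the bar fully effective, the cumulative count adds nothing without expansion. With every reached dose expanded it adds about 1.6 points at 5% (2.2 − 0.6), 6.8 at 10% (10.42 − 3.58) and 14 at 20% (31.9 − 17.5). These figures also assume that expansion goes ahead after such events. If only repeats of the same type of event count, both rules fire less often.

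It is tempting to quote the 6-6-6 contrast of 27% against 73% as the expected effect. The protocol does not support that: it applies only if escalation proceeds despite such events, and a 20% rate is far from the routine-laparoscopy risk that 4.5 expects. Nor is this a contradiction within the protocol. It is a design choice that fits its purpose poorly, to be considered rather than required.

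**What to change.** In 6.6.2, replace the condition on more than 2 patients at any dose level with: *in more than 2 patients cumulatively across all dose levels*. Keep a per-dose tally for reporting, because sphere and buffer volumes rise with dose. Whether an event poses an unacceptable risk stays a judgement, as now. Any lower threshold for the earliest patients is for the sponsor and SRC to decide.

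The cost is one phrase and a modestly higher chance of a halt: nil to about 1.6 percentage points at an assumed 5% rate if the bar on escalation works, and at most 5.1 points (5.8 − 0.7) if escalation proceeds regardless. A halt is not trivial, since restarting needs regulatory and ethics approval of a substantial amendment. The extra halts would arise only after three patients had SAEs already judged an unacceptable risk.

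### The dose-limiting toxicity rules name possibly and probably related events but leave out definitely related ones, so read literally the clearest product toxicity does not halt dosing

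*Protocol*

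**What the plan says.** Section 6.6.2 of the Protocol lists the DLTs. Any one of them triggers an ad hoc review by the Safety Review Committee (SRC), halts dosing and escalation, and is the study's stopping criterion. Restart is then tightly controlled: "Any proposal to restart dosing in the trial will require Regulatory Authorities and Ethics Committees approval of a substantial protocol amendment prior to implementation".

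Three of the DLT bullets are worded by causality:

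- Product SAE: "Any SAE that is considered possibly or probably related to SIG-001, which is deemed to pose unacceptable risk to study participants".
- Surgical SAE: "Any surgical SAE that is considered possibly or probably related to the anaesthesia or laparoscopic procedure", subject to two further conditions: "deemed to pose an unacceptable risk to study participants, and occurs in more than 2 patients at any dose level".
- Toxicity by grade: "Any Grade III-IV toxicity assessed as possibly or probably related to the study product".

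For grading and reporting, 6.6.2 points to Section 12: "All AEs/SAEs will be graded and reported as per Section 12 Safety and Adverse Events". Section 12.1.7 then defines five relationship categories, each with its own description: *Definitely*, *Probably*, *Possibly*, *Unlikely* and *Not Related*. It adds that possibly or probably related events count as related for regulatory reporting, that unlikely related events count as unrelated, and that an assessment the investigator omits is treated as *possibly* related until supplied.

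**The concern.** The causality scale and the rule that uses it do not match. The scale has three positive levels and the rule names the lower two. Taken literally, the DLT definition leaves out the level at which the investigator has no doubt that the product caused the event.

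This is the binding stopping rule of a first-in-human trial of a product that Section 12.3.3 describes as meant for permanent placement. At stake are the automatic halt and the requirement for regulatory and ethics approval of an amendment before restart. Both attach only to a listed DLT.

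**Working it through.** No arithmetic is involved beyond counting. The check sets the scale in 12.1.7 against each sentence that uses it.

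**Step 1. Does any sentence cover the top category?**

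| Sentence | Definitely | Probably | Possibly | Unlikely | Not related |
|---|---|---|---|---|---|
| 6.6.2, product SAE | no | yes | yes | no | no |
| 6.6.2, surgical SAE | no | yes | yes | no | no |
| 6.6.2, Grade III-IV toxicity | no | yes | yes | no | no |
| 12.1.7, counts as related | no | yes | yes | no | no |
| 12.1.7, counts as unrelated | no | no | no | yes | no |

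The first four sentences each name 2 of the 3 positive categories. The two reporting sentences in 12.1.7 together assign 2 + 1 = 3 of the 5 categories and leave 5 − 3 = 2 unassigned (*Definitely* and *Not Related*). No sentence says that *probably* includes *definitely*, or that the wording sets a floor.

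**Step 2. Does the missing word decide the outcome?** That depends on what else each DLT bullet requires.

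- Grade III-IV toxicity: no further condition, so the missing word alone decides.
- Product SAE: one further condition, a judgement of unacceptable risk.
- Surgical SAE: two further conditions, unacceptable risk and more than 2 patients at a dose level. That means at least 3 of the at most 6 patients that Section 6.3 allows per dose.

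**Step 3. Follow one event through the rule.** Take a Grade III-IV toxicity that meets no other DLT bullet.

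- Rated *possibly* or *probably* related: DLT, halt, amendment before restart.
- Rating omitted: defaulted to *possibly* under 12.1.7, so the same result.
- Rated *definitely* related: not a listed DLT, so neither the halt nor the amendment requirement applies.

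**Step 4. What else would catch it?**

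- Any death is a DLT whatever its cause. So is an overall pattern of change judged potentially related to the product, but that needs a pattern and not a single event.
- Section 12.2.2 requires SAE reports within 24 hours whatever the causality, and Section 11.1 adds: "Additionally, the SRC will review all SAEs in an ongoing manner". Both cover serious events only. Section 12.1.2 itself notes that an AE can be severe without being serious. Two of the listed Grade III-IV examples, persistent abdominal pain and persistent inhibitor titres, need not meet a seriousness criterion.
- Section 6.4 bars escalation when a clinically relevant safety issue is seen. It does not stop further dosing at the same level.
- Section 11.1 schedules SRC review of data to Week 8 or later in the first three patients, and to Week 4 or later in everyone after them, expansion patients included. This is scheduled review, and expansion patients need not be staggered (Section 6.4), so several may be dosed close together before it takes place.

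Apart from the death and pattern bullets, these routes give review and discretion, not the automatic halt.

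**The case against.** The best case on the other side runs as follows.

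1. *Probably Related* in 12.1.7 has no upper bound, so an event with no causal uncertainty also fits that description. The Protocol does not state that the categories are mutually exclusive.
2. Several passages point to a minimum threshold. Section 13.6.1 counts patients at their strongest relationship, a missing rating defaults upward to *possibly*, and the last DLT bullet speaks of potential relatedness. No investigator or SRC would treat a possible toxicity as a DLT and a certain one as not.
3. Thrombosis, peritonitis, adhesions or fibrosis, and FVIII activity above 150 IU/dL carry no causality wording of their own. If they are stand-alone bullets, they halt dosing whatever the attribution.
4. Section 6.6.1 has the SRC evaluate any unforeseen safety event, serious or not. During staggered dosing, Section 6.4 requires SRC review before the next patient is treated.
5. The 12.1.7 sentences apply only to regulatory reporting, where no lost report follows.

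Point 1 is strained. A five-level scale with a separate definition for each level, and a rule for counting the strongest, treats the levels as distinct. The Grade III-IV bullet also refers to the category as assessed.

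Point 2 is right about intent and is why the harm is limited, but the intent is nowhere written into the rule.

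Point 3 cannot be settled, because the text at hand does not show whether those items are examples under the Grade III-IV bullet. They are left out of the count.

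Point 4 narrows the gap but supplies review, not the halt or the amendment requirement.

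Point 5 stands: the 12.1.7 sentences neither cause nor cure the DLT gap, and the missing *Not Related* is editorial. They belong in the same correction because they repeat the omission.

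**Conclusion.** The inconsistency is real and should be fixed. As written, three DLT bullets in 6.6.2 and one sentence in 12.1.7 leave out the strongest causality category. For the Grade III-IV bullet that omission alone decides whether dosing halts.

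The practical gap is narrow: chiefly a single non-serious Grade III-IV toxicity, rated definitely related and meeting no other DLT bullet, which would reach the SRC only through scheduled or signal-driven review. The two SAE bullets have the same gap, but a halt under them also needs other conditions, and serious events reach the SRC anyway. No estimate, analysis set or endpoint is affected, and no SAE report is claimed to be lost.

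The conclusion rests on reading the five categories in 12.1.7 as distinct, which their separate definitions and Section 13.6.1 support. It does not depend on how the thrombosis, peritonitis, adhesion and high-FVIII items are nested, although the size of the gap in practice does.

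**What to change.** In the three causality-worded DLT bullets of 6.6.2 and in the 12.1.7 sentence on events that count as related, write *possibly, probably or definitely related*. In the 12.1.7 sentence on events that count as unrelated, write *unlikely related or not related*. Leave the unacceptable-risk condition, the more-than-2-patients condition and Section 13.6.1 unchanged.

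The cost is a few words in five sentences, with no added patients, visits or procedures.
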